#### **6.4.4 Duration of Response**

Duration of overall response: The duration of overall response is measured from the time measurement criteria are met for CR or PR (whichever is first recorded) until the first date that recurrent or progressive disease is objectively documented (taking as reference for progressive disease the smallest measurements recorded since the treatment started).

The duration of overall CR is measured from the time measurement criteria are first met for CR until the first date that recurrent disease is objectively documented.

Duration of stable disease: Stable disease is measured from the start of the treatment until the criteria for progression are met, taking as reference the smallest measurements recorded since the treatment started.

#### **6.4.5 Progression-Free Survival**

Progression-free survival (PFS) is defined as the duration of time from start of treatment to time of progression.

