### **2.2 Secondary Objectives**

- b. To assess if percentage change in FFLT PET/CT quantitative parameters (SUV max, or SUV peak or proliferative tumor volume) after 2 cycles of chemotherapy can predict progression free survival at 6 months and 1 year in patients with resectable, borderline resectable or locally advanced pancreatic adenocarcinoma.

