### **2.4 Endpoints**

Primary endpoint is to determine that a positive response (decrease on quantitative parameters) at an interim F FLT PET/CT (performed after 2 cycles of chemotherapy) is related to longer progression free survival and overall survival.

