## 6.0 Measurement of Effect

### 6.1 Antitumor Effect- Solid Tumors

Response and progression will be evaluated in this study using the new international criteria proposed by the Response Evaluation Criteria in Solid Tumors (RECIST) Committee. Changes in only the largest diameter (unidimensional measurement) of the tumor lesions are used in the RECIST v1.1 criteria.

This evaluation will be done at the CT or MRI by the end of chemotherapy and in follow up CT or MRI, performed as standard of care (up to 2 years). This information will be used for assessment of progression free survival at 6 months and at 1 year.

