#### 6.4.3 Evaluation of Best Overall Response

The best overall response is the best response recorded from the start of the treatment until disease progression/recurrence (taking as reference for progressive disease the smallest measurements recorded since the treatment started). The subjects best response assignment will depend on the achievement of both measurement and confirmation criteria.

Target Lesions	Non-Target Lesions	New Lesions	Overall Response	Best Response for this Category Also Requires:
CR	CR	No	CR	$\geq 4$ wks. confirmation
CR	Non-CR/Non-PD	No	PR	$\geq 4$ wks. confirmation
PR	Non-PD	No	PR	
SD	Non-PD	No	SD	Documented at least once $\geq 4$ wks. from baseline
PD	Any	Yes or No	PD	No prior SD, PR or CR
Any	PD*	Yes or No	PD	
Any	Any	Yes	PD	

\* In exceptional circumstances, unequivocal progression in non-target lesions may be accepted as disease progression.

Note: Subjects with a global deterioration of health status requiring discontinuation of treatment without objective evidence of disease progression at that time should be reported as “*symptomatic deterioration*”. Every effort should be made to document the objective progression even after discontinuation of treatment.

Note: If subjects respond to treatment and are able to have their disease resected, the patient’s response will be assessed prior to the surgery.

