## **9.0 STATISTICAL CONSIDERATIONS**

### **9.1 Study Design/Study Endpoints**

We anticipate to enroll 20 patients with biopsy proven pancreatic adenocarcinoma that are not eligible for resection by the time of the diagnosis. These patients are going to be treated with chemotherapy only or chemoradiation in selected cases. These patients will undergo an optional F FDG PET/CT (as standard of care clinical baseline) and F-FLT PET/CT before treatment (research baseline study), and after two cycles of chemotherapy (research early therapy assessment study).

For the F-FLT PET/CT analysis, SUV max, SUV peak and proliferative tumor volume will be measured by MIMvista software and compared between the two studies. Tumor size and extension will also be evaluated on CT images from the PET/CT study.

At completion of treatment (6 months after baseline FLT PET/CT) an anatomic study (MRI or CT) will be performed as standard of care in our institution to reassess the tumor and classify it as resectable or non-resectable. Also at 6 months, 1 year and 2 years after initial baseline scan, or before if clinically indicated, standard of care anatomic study (MRI or CT) will also be performed and will be reevaluated by RECIST criteria to determine stability versus progression of disease.

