## **9.3 Data Analyses Plans**

Primary outcome variable: The difference in SUVmax, SUVpeak and proliferative tumor volume between baseline and 2 cycles of chemotherapy will be correlated with overall survival at 1 and 2 years and with progression free survival at 6 months and at 1 year.

The primary outcome of the study is to establish which degree of change in the PET/CT quantitative parameters can predict patients overall survival and progression free survival. The SUVmax (representing the single voxel with the highest activity concentration), SUV peak (which is defined as the average SUV within a 1 cubic cm volume within the region of the tumor with the highest metabolic activity) and proliferative tumor volume of the pancreatic tumor will be measured.

Univariate and multiple cox regression model are going to be used. P-value less than 0.05 will be considered as statistical significant.

Secondary outcome variable: the difference in SUVmax, SUVpeak and proliferative tumor volume between baseline and 2 cycles of chemotherapy will be correlated with binary tumor outcome measured from MRI/CT (resectable versus non-resectable disease) at 6 month using logistic regression. A multiple logistic regression with stepwise selection algorithm will be used to select the most correlated variable(s). Areas under the ROC curve (AUC) and corresponding 95% confidence interval will be calculated for all models. Leave one out cross validation will be applied to avoid over-fit.

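### PFS in section 6.4.5 ends at progression only, so a death without documented progression is never an event and the endpoint is really time to progression

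*Combined protocol and SAP*

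**What the plan says.** Section 6.4.5 defines the endpoint: "Progression-free survival (PFS) is defined as the duration of time from start of treatment to time of progression". The clock start is clear, and the only terminating event is progression.

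Progression is an imaging finding. Sections 6.4.1 to 6.4.3 define it by growth of target lesions, new lesions or unequivocal worsening of non-target lesions. Section 6.1 describes the CT or MRI reads and adds: "This information will be used for assessment of progression free survival at 6 months and at 1 year". Section 9.1 schedules those scans: "Also at 6 months, 1 year and 2 years after initial baseline scan, or before if clinically indicated".

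A note in section 6.4.3 covers patients whose general health declines to the point of stopping treatment. Decline "without objective evidence of disease progression at that time should be reported as" symptomatic deterioration, a category separate from progressive disease. The note continues: "Every effort should be made to document the objective progression even after discontinuation of treatment".

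PFS has a prominent role. The secondary objective (2.2) asks whether FLT change "can predict progression free survival at 6 months and 1 year". Section 2.4 puts PFS into the primary endpoint, where response on the interim scan "is related to longer progression free survival and overall survival". Section 9.3 also names PFS with overall survival as a primary outcome and says of the method: "Univariate and multiple cox regression model are going to be used". It gives no event or censoring rule. The time and events table (5.2) collects survival status during follow-up, but no section gives death a role in PFS.

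**The concern.** PFS normally ends at progression or death, whichever comes first. Here the written definition leaves death out, and a Cox model needs every patient coded as an event or censored at a stated time. Take a patient who declines and dies at month 9 with no scan showing progression. For 1-year overall survival that patient has failed. For 1-year PFS the patient has not, and the plan does not say whether to censor, exclude or count the patient as progression-free.

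The design makes such cases possible. Scheduled progression imaging is sparse, and clinical decline without imaging evidence is placed outside progressive disease.

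Two things are at stake. Reported PFS at 6 months and 1 year would be too high by an amount that depends on an unstated coding choice. The models relating FLT change to PFS, in at most 20 patients, would lose events, and their censoring could be informative because death after undocumented decline is unlikely to be independent of progression.

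**Working it through.** **Text check.** The sections that use PFS or define or schedule progression are the Study Summary, 2.2, 2.4, 6.1, 6.4.1 to 6.4.5, 9.1 and 9.3. None counts death as a PFS event or states a censoring rule. Elsewhere, death appears in the disease background and the adverse-event text. The definition in 6.4.5 therefore stands alone.

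**The plan's own figure.** No PFS rate, event count or power is stated. The only calculation (9.2) is for a paired change in FLT SUV: (0.17 × 2.8016 / 0.124)² = 14.75, rounded up to 15, plus 5 for dropout and absent baseline uptake = 20. It reproduces by the normal approximation and does not depend on the PFS definition.

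**Effect of one such death before a landmark.** Let N be the number of patients and S the correct PFS at the landmark (progression or death), with no other censoring. Then S·N patients are truly event-free.

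- Counted as progression-free: (S·N + 1)/N − S = 1/N.
- Excluded: S·N/(N − 1) − S = S/(N − 1).
- Censored (Kaplan–Meier): S/(N − 1) if the death precedes every progression, rising to 1/N if it follows the last progression before the landmark.

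N is 20 (planned) or 15 (before the allowance). S = 30–60% is an assumption.

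| Handling | N = 20 | N = 15 |
|---|---|---|
| Counted progression-free | 1/20 = 5.0 points | 1/15 = 6.7 points |
| Excluded | 0.30/19 to 0.60/19 = 1.6–3.2 | 0.30/14 to 0.60/14 = 2.1–4.3 |
| Censored | 1.6–5.0 | 2.1–6.7 |

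Example: 20 patients, 10 progressions and 1 such death by 1 year. PFS is 9/20 = 45% with death as an event, 9/19 = 47.4% if the patient is excluded or censored before the first progression, and 10/20 = 50% if counted progression-free. A death after a landmark does not change PFS at that landmark.

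**How many such deaths (illustration only).** The documents give no rates, so these are assumptions: exponential times, median 8–12 months to progression and 5–8 months from progression to death, and a stated share of progressions found clinically when they occur. The rest are found at the next scheduled scan if the patient is still alive. Scans are at 6, 12 and 24 months, counted from start of treatment or from a baseline scan one month earlier (section 4.0 allows up to 30 days). Resection is not modelled. Simulation used 400,000 patients per scenario, comparing Kaplan–Meier with such deaths censored against progression or death.

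| Found clinically | Other-cause death per month | Such deaths per 20 by month 12 | PFS too high (points) |
|---|---|---|---|
| 75–90% | 0 | 0.2–1.1 | 0.4–3 |
| 75–90% | 0.25–0.5% | 0.6–1.9 | 1–6 |
| 75–90% | 1% | 1.7–2.5 | 4–9 |
| 50% | 0 or 1% | 1.0–3.7 | 2–9 at 6 months, 4–12 at 12 months |

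One scenario in full (medians 8 and 5 months, 75% found clinically, no other-cause death, scans from start of treatment): 6-month PFS 0.622 as written against 0.594, and 12-month PFS 0.385 against 0.352. At 75–90% detection and 0–1% other-cause death, events per 20 by month 12 are 8.6–12.6 as written and 9.9–13.7 with death counted. These ranges are not bounds.

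**Hazard ratio.** With an assumed binary predictor, a progression hazard ratio of 2, 75% detection and a 12-month horizon, results as written against progression-or-death were:

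- 1.89 against 1.99: medians 8 and 5, no other-cause death, poor responders dying twice as fast after progression.
- 1.99 against 1.80: medians 12 and 8, 1% other-cause death per month, no predictor effect after progression.

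The shift can go either way.

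**The case against.** The strongest reply is that time to progression is a coherent outcome for an early-response marker. Overall survival already counts every death, and adding deaths unrelated to FLT change can dilute the association sought, as in the 1.99 against 1.80 case. This is a fair argument for studying time to progression, but not for calling it PFS. The lower hazard ratio is the correct value for PFS in that scenario, and overall survival does not repair a mislabelled second endpoint.

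A second reply is that the shift is small against the study's precision. At PFS 50% with 20 patients the standard error is √(0.5 × 0.5/20) = 11 points, and the mildest scenarios give only 0.4–3 points. The plan also tests an association, not a landmark rate. This limits the importance of the point. However, the shift in the landmark rate is always upward, unlike sampling error.

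Third, clinically indicated scans and the instruction to pursue documentation will catch many progressions. They make undocumented deaths fewer but cannot exclude them.

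Finally, the name PFS conventionally implies death. The protocol does not rely on convention: it writes its own definition, and that definition omits death.

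**Conclusion.** The concern holds. As written, the endpoint is time to progression under the name PFS, and the handling of a death without documented progression is unspecified. Each such death before a landmark raises PFS there by 1.6–5.0 points with 20 patients, or 2.1–6.7 with 15, depending on handling. The 1/N figures need only the patient number; the lower ends also assume correct PFS of 30–60% and no other censoring. The total depends on how many such deaths occur, which the documents do not allow anyone to estimate, and is zero if there are none. For the planned Cox analysis, the loss of events and possible informative censoring are real, but no direction of bias can be claimed. Overall survival and the sample size are untouched. This should be corrected before PFS is analysed, because PFS is the secondary endpoint and is also named as primary in 2.4 and 9.3.

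**What to change.** Rewrite 6.4.5 so that PFS runs from start of treatment to first RECIST progression or death from any cause, whichever is first, with patients alive and progression-free censored at their last adequate tumour assessment. State what counts as an adequate assessment, and refer to this definition in 9.3. If the team also wants time to progression as a marker outcome, it should be reported under that name with its own rule for deaths.

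The core change is one sentence. It needs a written amendment with IRB approval under 10.8, but no new data, because survival status is already collected at follow-up (5.2). The price is less favourable PFS figures and, where deaths are unrelated to FLT change, possibly a weaker association with PFS.

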### **6.5 Safety/tolerability**

Analyses will be performed for all subjects having received at least one dose of study drug. The study will use the CTCAE version 4.0 for reporting of non-hematologic adverse events (<http://ctep.cancer.gov/reporting/ctc.html>) and modified criteria for hematologic adverse events.

## **7.0 ADVERSE EVENTS**

### **7.1 Adverse Event Monitoring**

Adverse event data collection and reporting, which are required as part of every clinical trial, are done to ensure the safety of subjects enrolled in the studies as well as those who

---

will enroll in future studies using similar agents. Adverse events are reported in a routine manner at scheduled times during a trial. Additionally, certain adverse events must be reported in an expedited manner to allow for optimal monitoring of subject safety and care.

All subjects experiencing an adverse event, regardless of its relationship to study drug, will be monitored until:

- the adverse event resolves or the symptoms or signs that constitute the adverse event return to baseline;
- any abnormal laboratory values have returned to baseline;
- there is a satisfactory explanation other than the study drug for the changes observed; or
- death.

### **Definition**

Adverse Events will be reported as indicated by the appropriate following table (see below).

An adverse event is defined as any untoward or unfavorable medical occurrence in a human research study participant, including any abnormal sign (for example, abnormal physical exam or laboratory finding), symptom, clinical event, or disease, temporarily associated with the subject's participation in the research, whether or not it is considered related to the subject's participation in the research.

Adverse events encompass clinical, physical and psychological harms. Adverse events occur most commonly in the context of biomedical research, although on occasion, they can occur in the context of social and behavioral research. Adverse events may be expected or unexpected.

### **Severity**

Adverse events will be graded by a numerical score according to the defined NCI Common Terminology Criteria for Adverse Events (NCI CTCAE) and version number specified in the protocol. Adverse events not specifically defined in the NCI CTCAE will be scored on the Adverse Event log according to the general guidelines provided by the NCI CTCAE and as outlined below.

- Grade 1: Mild

- Grade 2: Moderate
- Grade 3: Severe or medically significant but not immediately life threatening
- Grade 4: Life threatening consequences
- Grade 5: Death related to the adverse event

### **Serious Adverse Events**

ICH Guideline E2A and the UTSW IRB define serious adverse events as those events, occurring at any dose, which meets any of the following criteria:

- Results in death
- Immediately life-threatening
- Results in inpatient hospitalization or prolongation of existing hospitalization
- Results in persistent or significant disability/incapacity
- Results in a congenital anomaly/birth defect
- Based upon appropriate medical judgment, may jeopardize the subject's health and may require medical or surgical intervention to prevent one of the other outcomes listed in this definition.

Note: A “Serious adverse event” is by definition an event that meets *any* of the above criteria. Serious adverse events may or may not be related to the research project. A serious adverse event determination does not require the event to be related to the research. That is, both events completely unrelated to the condition under study and events that are expected in the context of the condition under study may be serious adverse events, independent of relatedness to the study itself. As examples, a car accident requiring overnight hospitalization would be a serious adverse event for any research participant; Likewise, in a study investigating end-stage cancer care, any hospitalization or death which occurs during the protocol-specified period of monitoring for adverse and serious adverse events would be a serious adverse event, even if the event observed is a primary clinical endpoint of the study.

All serious adverse events occurring within a 24-hour period post-FLT infusion will be recorded.

**Unanticipated Problems Involving Risks to Subjects or Others (UPIRSOs):**

The term “unanticipated problem” is found, but not defined in the regulations for the Protection of Human Subjects at 45 CFR 46, and the FDA regulations at 21 CFR 56. Guidance from the regulatory agencies considers unanticipated problems to include any incident, experience, or outcome that meets each of the following criteria:

- Unexpected (in terms of nature, severity or frequency) AND
- Definitely or probably related to participation in the research AND
- Serious or a possible unexpected problem in that the research places subjects or others at greater risk of harm than was previously known or recognized. Note: Any serious adverse event would always suggest a greater risk of harm.

**Follow-up**

All adverse events will be followed up according to good medical practices.

**Reporting**

The UTSW IRB requires reporting of all UPIRSOs according to the guidance below. For participating centers other than UTSW, local IRB guidance should be followed for local reporting of serious adverse events. All SAEs occurring during the protocol-specified monitoring period should be submitted to the UTSW study team within 2 business days of the center learning of the event.

7.2.3.1 UPIRSOs occurring on the study require expedited reporting, and are submitted to the UTSW IRB through the UTSW eIRB by the UTSW study team and to the SCCCC DSMC Coordinator. Hardcopies or electronic versions of the eIRB report; FDA Form #3500A forms, or other sponsor forms, if applicable; and/or any other supporting documentation available should be submitted to the UTSW study team and will be forwarded to the DSMC Coordinator. The DSMC Coordinator forwards the information onto the DSMC Chairman who determines if immediate action is required. Follow-up eIRB reports, and all subsequent SAE documentation that is available are also submitted to the DSMC Chair who determines if further action is required. (See Appendix IV of the SCCCC DSMC Plan for a template Serious Adverse Event Form which may be utilized when a sponsor form is unavailable and SAE submission to the eIRB is not required).

All serious adverse events which occur on research subjects on protocols for which the SCCCC is the DSMC of record require reporting to the DSMC regardless of whether IRB reporting is required. Hardcopies or electronic versions of the FDA Form #3500A forms, or other sponsor forms, if applicable; and/or any other supporting documentation available should be forwarded to the DSMC Coordinator.

Telephone reports to:  (Investigator/study team: [name], [contact])
Written reports to:  (Investigator/study team: [name], [contact], [contact], email: [contact])
UTSW SCC Data Safety Monitoring Committee Coordinator  Email: [contact]  [contact] or deliver to BLB.306
UTSW Institutional Review Board (IRB)  Submit via eIRB with a copy of the final sponsor report as attached supporting documentation

### **SAEs**

Serious adverse events (SAEs) for studies where Simmons Cancer Center (SCCC) Data Safety Monitoring Committee (DSMC) is the DSMC of record, requires reporting to the DSMC coordinator within 2 working days of PI awareness, or as described in the protocol.

### **Unanticipated Problems Involving Risks to Subjects or Others (UPIRSOs)**

**Local Serious Adverse Event UPIRSOs require reporting to the UTSW IRB within 48 hours of PI awareness of the event (life threatening or fatal events experienced by subjects** Steps to Determine If an Adverse Event Requires Expedited Reporting

**Step 1:** Identify the type of adverse event using the NCI Common Terminology Criteria for Adverse Events (CTCAE v4).

Step 2: Grade the adverse event using the NCI CTCAE v4.

Step 3: Determine whether the adverse event is related to the protocol therapy

Attribution categories are as follows:

- Definite – The AE *is clearly related* to the study treatment.
- Probable – The AE *is likely related* to the study treatment.
- Possible – The AE *may be related* to the study treatment.
- Unrelated – The AE *is clearly NOT related* to the study treatment.

Step 4: Determine the prior experience of the adverse event.

Expected events are those that have been previously identified as resulting from administration of the agent. An adverse event is considered unexpected, for expedited reporting purposes only, when either the type of event or the severity of the event is not listed in:

- the current known adverse events listed in the Agent Information Section of this protocol;
- the drug package insert;
- the current Investigator's Brochure

